9.5 Rescue treatment

If medically necessary (i.e. to control intolerable worsening of AD symptoms), rescue treatment of AD may be provided to the subject at the discretion of the investigator. If possible, the investigator should attempt to limit the first step of rescue treatment to topical treatment and escalate to systemic treatment if the subject does not respond adequately to topical rescue treatment.

Topical rescue treatment

In this trial, topical rescue treatment of AD consists of TCS and TCI. Subjects provided with topical rescue treatment between first dose of IMP and Week 16 may continue treatment with the IMP and remain in the trial with no change to the visit schedule nor trial assessments/procedures.

Systemic rescue treatment.

If the subject is provided with systemic rescue treatment of AD at any time during the treatment period, treatment with IMP will immediately and permanently be discontinued (see also Section 9.7 for prohibited medications).

Before administering topical or systemic rescue treatment, the investigator may conduct efficacy and safety assessments (e.g. disease severity scores [EASI, vIGA-AD, and SCORAD], AEs, safety laboratory samples, PK blood sample, and concomitant medications/concurrent procedures). However, to safeguard subject safety and well-being, the assessments should only be conducted if the subject's health permits. To further attend to subject safety and well-being, an unscheduled visit, scheduled earlier than the next planned visit, may be arranged to administer the topical or systemic rescue treatment.

If the subject is permanently discontinued from IMP due to use of systemic rescue medication, every effort must be done to monitor the subject as described in Section 10.3.

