9.7 Prohibited medications and procedures

The medications and procedures listed in [Panel 7](#) and [Appendix 8](#) are prohibited during the trial. Prohibited medications and procedures prior to and during screening are also listed in [Section 8.3](#).

If prohibited medications are used during the trial, they must be recorded as concomitant medication in the eCRF ([Section 9.6](#)).

Prohibited topical medications used as rescue treatment of intolerable AD symptoms are allowed ([Section 9.5](#)). Such use of prohibited topical medications does not constitute a protocol deviation.

Panel 7: Prohibited medications and procedures

Medication	Prohibited from	Prohibited to
Allergen immunotherapy	Within 5 half-lives prior to baseline	Week 17 (safety follow-up)
H4R antagonist (oral)	Within 6 months prior to baseline (exclusion criterion 3)	Week 17
Immunoglobulin or blood product	Within 5 half-lives prior to baseline	Week 17
Investigational agents other than LEO 152020	Within 4 weeks or 5 half-lives prior to baseline, whichever is longer	Week 17
Live (attenuated) vaccine	Baseline	Week 17
Medication for which CCI is a known side effect	Within 5 half-lives prior to screening	Week 17
Medications known to inhibit the CCI ^a	Within 5 half-lives prior to baseline	Week 17
Medications known to inhibit the CCI ^b	Within 5 half-lives prior to baseline	Week 17
Medications known to inhibit the CCI ^c	Within 5 half-lives prior to baseline	Week 17
Retinoids	Within 4 weeks prior to baseline	Week 17
Systemic AD treatments	Within 4 weeks or 5 half-lives prior to baseline, whichever is longer	Week 17

Medication	Prohibited from	Prohibited to
Systemic anti-histamines ^d	Within 4 weeks or 5 half-lives prior to baseline, whichever is longer	Week 17
Systemic corticosteroids ^e	Within 4 weeks or 5 half-lives prior to baseline, whichever is longer	Week 17
Systemic immunosuppressive/immunomodulatory treatment (e.g. azathioprine, cyclosporine, dupilumab (or other biologics), interferon-gamma, JAK inhibitors, methotrexate, mycophenolate mofetil)	Within 4 weeks or 5 half-lives prior to baseline, whichever is longer	Week 17
TCS/TCI, except if used as rescue treatment	Week -1	Week 16 (end of treatment)
Other topical AD treatments	Week -1	Week 17
Topical antibiotics ^f	Week -1	Week 16
Procedure	Prohibited from	Prohibited to
Bleach bath	Within 4 weeks prior to baseline	Week 16
UVA, UVA1, UVB, NBUVB, PUVA therapy, other phototherapy, or tanning beds	Within 4 weeks prior to baseline	Week 17

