10.2 Reasons for permanent discontinuation of investigational medicinal product

Subjects will permanently discontinue IMP in the event of:

- Evidence of pregnancy.
- An AE that, in the opinion of the investigator or sponsor's medical expert, contraindicates further dosing.
- Initiation of systemic rescue treatment of AD.
- Initiation of prohibited medication (except topical medications used as rescue treatment of AD) which cannot be safely replaced by other non-prohibited medications.
- QTcF >500 ms or increase in QTcF from baseline >60 ms.
- Other reasons, at the discretion of the investigator. If other, a specification should be provided.

Reporting in eCRF

The primary reason for permanent discontinuation of IMP must be recorded in the subject's medical record and on the end of treatment form in the eCRF where the following options are available:

- Death.
- Pregnancy.
- Adverse event (if adverse event, a specification must be provided).
- Lack of efficacy. If lack of efficacy, a specification of the reason for lack of efficacy of the IMP must be provided:
 - Lack of efficacy on itch.
 - Lack of efficacy on visible AD symptoms.
 - Lack of efficacy on both itch and visible AD symptoms.
 - Other (if other, a specification must be provided).
- Withdrawal by subject.
- Lost to follow-up.
- Other (if other, a specification must be provided).

In case the primary reason is adverse event, the AE in question will be linked to the permanent discontinuation of IMP. To support the statistical analysis, it will also be recorded if the permanent discontinuation of IMP was due to the COVID-19 pandemic.

For reasons for withdrawal from the trial, see in Section [11.8](#), End of trial form.

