Abbreviations: AD = atopic dermatitis; ; COVID-19 = corona virus disease 2019; EASI = Eczema Area and Severity Index; IE = intercurrent events; IMP = investigational medicinal product.

THIS DOCUMENT CONTAINS CONFIDENTIAL INFORMATION AND MUST NOT BE COPIED OR MADE AVAILABLE TO ANY THIRD PARTY WITHOUT THE PRIOR WRITTEN CONSENT OF THE LEO PHARMA GROUP

For the evaluation of efficacy, the following intercurrent events are considered to affect the interpretation of the measurements of the endpoint/variable:

Non-pandemic related intercurrent events

- **Initiation of rescue treatment:** This event occurs when a subject initiates rescue treatment. This event can occur at the discretion of the investigator. The timing of the event is defined as the date of initiation of the rescue treatment recorded in the eCRF and the event will be handled without assessing relatedness to the COVID-19 pandemic.
- **Permanent discontinuation of IMP independently of the COVID-19 pandemic:** This event occurs when a subject permanently discontinues IMP independently of the pandemic. This event can occur at the subject's own initiative, or at the discretion of the investigator or the sponsor. The timing of the event is defined as the date of permanent discontinuation of IMP recorded in the eCRF.

Pandemic related intercurrent events

- **Permanent discontinuation of IMP due to the COVID-19 pandemic:** This event occurs when a subject permanently discontinues IMP due to circumstances related to the pandemic and is not attributed to lack of efficacy or randomized treatment features considered unacceptable by the subject.

Depending on the estimand strategy selected, the occurrence of an intercurrent event may be ignored, lead to the exclusion of data observed after the occurrence of the event, be accounted for in the definition of a composite endpoint, or restrict the relevant observation window to the time prior to the occurrence of the intercurrent event, as described below.

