14.3.8.1 Primary estimand

The primary estimand will use the *hypothetical strategy* to handle the occurrence of intercurrent events. The estimand attempts to quantify the effect of treatment, in the hypothetical scenario, where subjects do not permanently discontinue IMP for any reason and where rescue medication is not made available prior to Week 16.

For subjects observed to experience an intercurrent event, the potential outcomes under the envisioned hypothetical scenario, are assumed to follow the outcome distribution for subjects in the same treatment group, who did not experience an intercurrent event.

The primary estimand assesses the expected benefit of the treatment when adhering to the treatment regimen in the context of the specified hypothetical scenario.

Main analysis

Data collected after permanent discontinuation of IMP, regardless of reason, or the initiation of rescue treatment will be excluded from the analysis and "treated as missing".

The endpoint will be analyzed using a MMRM. The model will include treatment, visit, visit by treatment interactions, and region (Japan, non-Japanese countries) as factors and be adjusted for the baseline EASI score as a covariate. The covariance matrix will be assumed to have an unstructured form and the Kenward-Roger approximation will be used to estimate the denominator degrees of freedom. Missing data, including data excluded due to the occurrence of an intercurrent event, is assumed to be MAR. The estimated LS-mean treatment differences, based on the observed margins, will be presented with 95% CIs and nominal p-values at each visit. The primary comparison is the treatment difference at Week 16, between the CCI and placebo groups.

Sensitivity analysis

The following sensitivity analyses will assess the robustness of the results of the main analysis with respect to the underlying statistical assumptions. The impact of the missing data assumptions on data excluded after the occurrence of an intercurrent event/due to the pandemic will not be considered in the sensitivity analyses, as the MAR assumption is aligned with the envisioned hypothetical scenario.

- Sensitivity analysis 1: Exclusion of subjects with monotone missing data at Week 1

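### Prohibited AD treatment not recorded as rescue, used while IMP continues, is not an intercurrent event in 14.3.8, so later EASI stays in the primary analysis as on-regimen data

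*Combined protocol and SAP*

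**What the plan says.** Section 14.3.8 introduces its list with the words "the following intercurrent events are considered to affect the interpretation of the measurements of the endpoint/variable". Three events follow: initiation of rescue treatment, permanent discontinuation of IMP unrelated to COVID-19, and permanent discontinuation because of COVID-19. The rescue entry reads "This event occurs when a subject initiates rescue treatment. This event can occur at the discretion of the investigator", and the event is dated from the rescue start date in the eCRF.

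The main analysis in 14.3.8.1 follows that list: "Data collected after permanent discontinuation of IMP, regardless of reason, or the initiation of rescue treatment will be excluded from the analysis". Panel 19 marks observed data from a subject with no intercurrent event as used under all three estimands. Section 14.3.10 sets non-response in the binary endpoints for rescue, IMP discontinuation or missing data only.

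Rescue is described in 9.5: for intolerable worsening, "rescue treatment of AD may be provided to the subject at the discretion of the investigator", with TCS and TCI as the topical options. Section 9.7 adds "Prohibited topical medications used as rescue treatment of intolerable AD symptoms are allowed". Panel 7 then prohibits two further categories that are not rescue: "TCS/TCI, except if used as rescue treatment" and "Other topical AD treatments". The stated consequence of prohibited use is an entry as concomitant medication. Section 10.2 makes it a reason to stop IMP only in this case: "Initiation of prohibited medication (except topical medications used as rescue treatment of AD) which cannot be safely replaced" by a permitted drug.

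**The concern.** The listed events are chosen because they change what a later EASI value means. An active non-trial treatment for AD does that whether the investigator supplied it or the subject took it from the cupboard. As written, the same corticosteroid leads to censoring in the first case and, if it is not recorded as rescue, to retention in the second.

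Such use is foreseeable. Subjects stop topical treatment at Week -1, roughly 29% receive placebo for up to 16 weeks, and rescue is reserved for intolerable worsening. A flare short of that leaves room for self-treatment.

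At stake is the meaning of the primary estimate, which is presented as the expected benefit when subjects keep to the regimen. The second supplementary estimand and the responder endpoints share the gap. The first supplementary estimand does not: under treatment policy, keeping the data is correct. The two sensitivity analyses in 14.3.8.1 address subjects without post-baseline EASI and the form of the baseline covariate, so neither would reveal the problem.

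**Working it through.** **Rule trace.** Take two subjects who use the same TCS for AD in Week 8 and stay on IMP.

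| Rule | Provided by the investigator as rescue | Self-applied, not recorded as rescue |
|---|---|---|
| Rescue event (14.3.8) | Yes | No |
| IMP stopped (10.2) | No | Not if a permitted substitute is safe |
| Panel 19 row | Rescue, observed | No intercurrent event, observed |
| Primary MMRM | Treated as missing | Used |
| First supplementary estimand | Used | Used |
| Second supplementary estimand | Imputed as non-response | Used |
| Responder endpoints (14.3.10) | Non-responder | Observed status |

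The right-hand column is the gap.

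**Arm sizes.** 224 subjects in a 4:3:3:4 ratio give 224 × 4/14 = 64 and 224 × 3/14 = 48 as expected sizes. Panel 17 is consistent with these, although its simulation inputs are blacked out and its absolute level cannot be rebuilt. Taking 90.8% power at 64 vs 64 (two-sided 5%, normal approximation) implies a standardised effect of 0.581. That effect at 48 vs 64 gives 86.1% (stated 85.3%), and gatekeeping with Hochberg gives 79.3% by simulation (stated 79.4%). These figures support the arm sizes only. They do not measure the effect of the gap.

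**Leverage on a responder rate.** One subject counts for at most 1/64 = 1.6 percentage points or 1/48 = 2.1 points.

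**Leverage on the mean difference.** Assume the non-trial treatment adds k times the true IMP effect, with k between 0 and 1 (an assumption; the documents give no value). The shift per net affected subject is k/n of the effect:

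- one net extra user on placebo (n = 64) shrinks the difference by k × 1.6%;
- one net extra user on active enlarges it by k × 1.6% (n = 64) or k × 2.1% (n = 48).

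At k = 0.5 these become 0.8%, 0.8% and 1.0%.

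**Cost of censoring instead.** Suppose m Week 16 values are lost from one arm and earlier visits and covariates recover nothing. The SE ratio is then:

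- 64 vs 64: √(1/(64−m) + 1/64) / √(2/64) = 1.0040 for m = 1 and 1.0165 for m = 4;
- 48 vs 64, lost from the arm of 48: √(1/(48−m) + 1/64) / √(1/48 + 1/64) = 1.0061 for m = 1 and 1.0256 for m = 4.

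The MMRM does use earlier visits, so these ratios are on the pessimistic side.

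**The case against.** The strongest reply is that the estimand is coherent on its own terms. Panel 18 spells out adherence by two conditions, no permanent discontinuation of IMP and no rescue, and 14.3.8.1 repeats them. The plan never claims to target a trial free of all deviations. This stands: a reader might infer that the analysis contradicts its own estimand, and the documents do not support that. The point is that the list is narrower than its stated reason.

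Second, the uncovered group may be small. Section 9.6 asks of any medication whether it is rescue for AD and sets no intolerability threshold. Appendix 9 speaks of rescue medication used by the subject. Section 9.7 allows prohibited topicals as rescue, so a PDE4i or topical JAK inhibitor given for an intolerable flare would plausibly be recorded as such. IMP may also be stopped at the investigator's discretion under 10.2. This stands too, and limits the concern to use that is not recorded as rescue.

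Third, there are routes for dealing with it. Section 14.2 provides for documented decisions on subject data before unblinding, 14.3.1 for blinded review and a final SAP, and Appendix 3D for assessment of deviations. These are general and state no rule for this case. Later SAP text could close the gap, so the documents show silence and not that the case will go unhandled.

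A reader might also infer lost power or an estimate tilted towards the drug. Neither follows: no rate of such use is given, and the sign depends on which arm has more of it.

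Finally, censoring after one brief application discards real data, and a sensitivity analysis might seem more proportionate. But the plan already treats any topical rescue this way, and a sensitivity analysis would need the same definition and listing.

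**Conclusion.** The concern holds in a limited form and is minor. AD-active treatment that Panel 7 prohibits, that is not recorded as rescue and that is used while IMP continues leaves later EASI in the primary MMRM and triggers no non-response in the second supplementary estimand or the responder endpoints. Those last two are supplementary and exploratory; the tested hypotheses rest on the MMRM.

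Frequency, direction and size cannot be determined from the documents, and the effect may be negligible. More use on placebo would shrink the estimated difference; more use on active would enlarge it. The leverage figures are per net affected subject and rest on the expected arm sizes and an assumed k. Confidence is medium, because it depends on how sites complete the rescue item and on SAP detail not in the supplied text.

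**What to change.** In 14.3.8 and the SAP, extend the rescue intercurrent event to the first use, after the first IMP dose and before the Week 16 visit, of any Panel 7 AD-active treatment given for AD:

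- TCS and TCI;
- other topical AD treatments, such as PDE4i or topical JAK inhibitors;
- systemic AD treatments, systemic corticosteroids and immunosuppressants;
- phototherapy.

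Apply it whatever the eCRF rescue item says, and date it from the recorded start date. Identify cases by blinded review of the medication and procedure records collected under 9.6, completed before unblinding. Exclude emollient and uses that Panel 7 permits: for example topical antibiotics on small lesional areas, locally administered anti-histamines, and inhaled or intranasal steroids within the allowed dose. The rule on continuing IMP need not change.

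The cost is one definition and one blinded listing, with no new data collection. The downside is a few more EASI values treated as missing under MAR and a few more imputed non-responders. Under the pessimistic assumption above, the SE rises by about 0.4 to 0.6% for one lost Week 16 value and by 1.7 to 2.6% for four.

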14.3.8.1 Primary estimand

The primary estimand will use the *hypothetical strategy* to handle the occurrence of intercurrent events. The estimand attempts to quantify the effect of treatment, in the hypothetical scenario, where subjects do not permanently discontinue IMP for any reason and where rescue medication is not made available prior to Week 16.

For subjects observed to experience an intercurrent event, the potential outcomes under the envisioned hypothetical scenario, are assumed to follow the outcome distribution for subjects in the same treatment group, who did not experience an intercurrent event.

The primary estimand assesses the expected benefit of the treatment when adhering to the treatment regimen in the context of the specified hypothetical scenario.

Main analysis

Data collected after permanent discontinuation of IMP, regardless of reason, or the initiation of rescue treatment will be excluded from the analysis and "treated as missing".

The endpoint will be analyzed using a MMRM. The model will include treatment, visit, visit by treatment interactions, and region (Japan, non-Japanese countries) as factors and be adjusted for the baseline EASI score as a covariate. The covariance matrix will be assumed to have an unstructured form and the Kenward-Roger approximation will be used to estimate the denominator degrees of freedom. Missing data, including data excluded due to the occurrence of an intercurrent event, is assumed to be MAR. The estimated LS-mean treatment differences, based on the observed margins, will be presented with 95% CIs and nominal p-values at each visit. The primary comparison is the treatment difference at Week 16, between the CCI and placebo groups.

Sensitivity analysis

The following sensitivity analyses will assess the robustness of the results of the main analysis with respect to the underlying statistical assumptions. The impact of the missing data assumptions on data excluded after the occurrence of an intercurrent event/due to the pandemic will not be considered in the sensitivity analyses, as the MAR assumption is aligned with the envisioned hypothetical scenario.

- Sensitivity analysis 1: Exclusion of subjects with monotone missing data at Week 1
Subjects with monotone missing data from Week 1 onwards are automatically excluded from the analysis. Although under the MAR assumption, the estimator of the treatment effect based on a likelihood analysis of a MMRM is unbiased, such exclusions run contrary to the intent of the FAS.

This sensitivity analysis will assess the robustness of the results of the main analysis with regards to the exclusion of subjects with no observed post-baseline EASI assessments. The analysis will include all randomized subjects regardless of whether a subject has observed post-baseline EASI score assessments. To assess the impact of excluding subjects with no post-baseline EASI score assessments from the analysis, the LS-mean treatment contrasts for the MMRM specified in the main analysis, will be estimated using the mean baseline EASI score and the proportion of subjects from each region based on the FAS.

- Sensitivity analysis 2: Functional form of the baseline EASI score covariate

This sensitivity analysis will assess the robustness of the results of the main analysis with respect to the assumed linear relationship between the mean change in EASI score from baseline to Weeks 1-16 and the baseline EASI score. Additional details for each sensitivity analysis will be specified in the SAP.

